**Schema**

For Patients with Probable Alzheimer's Disease based on NINCDS-ADRDA Criteria and having MMSE scores of between 10 - 20	
Number of Patients	30
Randomization	N/A
Screening/Baseline Testing	
The following tests/evaluation will be completed prior to initiation of treatment
 
 
1) MMSE
 
2) ADAS-Cog
 
3) History and Physical
 
4) Amyvid PET Scan
 
5) Toxicity Evaluation using CTC version 5.0/RTOG for following sites Skin, Eye, Ear and CNS
 
6) QOL-AD and QUALID assessment
 

Imaging Requirements	An Amyvid PET Scan will be required prior to treatment and at 4 months following completion of therapy. These scans will be read by the study designated board certified nuclear radiologist.
Treatment Procedure	Patients will receive whole brain irradiation using standard external beam techniques. The initial 15 patients will be treated at Dose Level 1 (5 x 200 cGy). If after the last patient in the first treatment group has been followed for 12 months and there have been no events that cause stoppage of the trial, the second group of patients will be enrolled at Dose Level 2 (10 x 200 cGy). All patients will receive 1 treatment per day on consecutive days excluding weekends
Trial Visits and Follow-Up	All patients will be followed as per Study calendar. Scheduled post treatment visits are at 6 weeks 3, 4, 6, and 12 months

Stopping Rules	
This Study will be stopped for any of the following reasons
 
 
1) Any patient death attributed to treatment
 
2) Any patient who develops a Grade IV adverse event
 
3) More than 3 of 15 patients who develop a Grade 3 adverse event as per CTCAE v.5.0 in either group
 
4) 50% or more of patients in either group have no change or increase in amyloid based on Amyvid PET Scan
 
5) 5 patients that show greater than 4 point deterioration in MMSE in two consecutive cognition evaluations
 
6) 5 patients that show mean increases greater than 7 on ADAS-Cog scale.
 

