### **3.9. Radiation On-Treatment Monitoring and Adverse Events**

Radiotherapy will be continued without interruption if at all possible as prescribed. If the sum of total radiotherapy interruptions exceeds seven normally scheduled treatment days, the treatment will be considered an unacceptable deviation from the protocol. This patient should

be reported to the principal investigator, and the patient will not be considered for final data analysis. Patients who do not complete a complete, total course of study radiotherapy will be replaced in the study in order to have 15 evaluable patients in each arm.

Patients will be monitored weekly by the treating radiation oncologist for the duration of radiotherapy and at regular intervals following radiotherapy. Scheduled post treatment visits are at 6 weeks, 3, 6 and 12 months. At each visit, the patient will undergo an interval history and physical exam and completion of Common Terminology Toxicity Criteria (Version 5.0), and RTOG toxicity scoring to assess any toxicity associated with this study. The RTOG toxicity scoring is done as radiation/oncology standard of care at Beaumont. This will include not only the effects on the CNS but any general adverse effects which may or may not be related to the treatment delivered. Each patient will be assigned a baseline score for skin, eye, ear and CNS and this will be monitored and evaluated during and after treatment for both acute and late toxicity. All adverse events will be recorded on an Adverse Event Reporting Form. The known risks associated with whole brain irradiation at the dose levels described may include, but are not limited to 1) hair loss, 2) decreased hearing, 3) nausea, 4) vomiting and 5) visual changes and 6) skin reactions. The grade or severity of adverse event that is common with the planned radiation dose for this trial based on the RTOG Common Toxicity Criteria are skin (Grade 1), CNS (Grade 1), ocular (Grade 0) and brain (Grade 1). All related/possibly related Grade >3 Toxicities will be reported as unexpected in severity to the IRB and monthly to the DSMB.

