### **3.10. Cognitive Assessment and Quality of Life Assessment During Treatment**

The Mini Mental Exam and ADAS-Cog are the two most commonly used tests of cognition in Alzheimer's Disease [58]. After treatment these tests will be administered by study designated, trained professional at 6 (+1) weeks, 3 (+1) months, 6 (+1) months and 12 months. Given that the ADAS-Cog is not used routinely in clinical practice (but rather a research assessment) and that the personnel involved may not necessarily be doing other studies requiring ADAS-Cog, it will not be possible to blind the professional doing the testing. The ADAS-Cog yields a single score that reflects the arbitrary weighting of performance in several cognitive domains including learning, language and spatial cognition but does not address executive function. A normal score for someone who does not have Alzheimer's or another type of dementia is 5; the greater

the dysfunction, the greater the score [59]. The properties of the ADAS-Cog are well understood; there is a curvilinear relationship between disease severity and rate of change on the ADAS-Cog. In a large clinical trial the baseline score for placebo-treated patients in the ADAS-Cog range of 13 to 26 was  $24.2 \pm 9.4$  and this increased to  $29.9 \pm 13.7$  representing a decline of  $5.7 \pm 8.2$  points over 1 year [60]. In this trial, a significant benefit in the active group was considered to be a 50% reduction in cognitive decline as indicated by change in ADAS-Cog score compared with the placebo group. In this study, patients who have an increase of no more than 50% (~3 points) on the ADAS-Cog at the end of treatment will be considered responders. This is equivalent to a delay in decline of about 6-8 months. Longitudinal analysis will be carried out for each individual patient using a fixed quadratic effect of time, dependent on the baseline level of ADAS-Cog, i.e., an interaction of baseline ADAS-Cog and the quadratic component of time.

The MMSE is a commonly used 30-point scale for assessing cognitive function in the domains of orientation, registration, attention and calculation, recall, language, and praxis. A MMSE score of 10 to 20 suggests moderate dementia. On average, the MMSE score of a person with moderate dementia declines about three to four points in a 12-month period. A similar analysis to that described above for the ADAS-Cog test will be carried out taking into account time and baseline MMSE score.

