### **3.12 Stopping Rules**

This study will be stopped for any of the following reasons

- 1) Any patient death attributed to treatment
- 2) Any patient who develops a Grade IV adverse event
- 3) More than 3 of 15 patients who develop a Grade 3 adverse event as per CTCAE v.5.0 in either group
- 4) 50% or more patients in either group have no change or increase in amyloid based on Amyvid PET Scan

- 5) 5 patients that show greater than 4 point deterioration in MMSE in two consecutive cognition evaluations
- 6) 5 patients that show increases greater than 7 on ADAS-Cog scale.

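### Stopping rule 6 (ADAS-Cog) has two mandatory wordings that can decide differently; under section 3.12's wording, the natural decline the protocol quotes would probably meet it

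*Combined protocol and SAP*

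**What the plan says.** Section 3.12 and the Schema each list six stopping reasons, and in both lists any one of them stops the study. Item 6 differs by one word:

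- Section 3.12: "5 patients that show increases greater than 7 on ADAS-Cog scale".
- Schema: "5 patients that show mean increases greater than 7 on ADAS-Cog scale".

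Neither version names a visit, a group or a confirmation requirement, and the Schema does not say what the mean is taken over. Neighbouring items are more specific. Item 3 reads "More than 3 of 15 patients who develop a Grade 3 adverse event as per CTCAE v.5.0 in either group", item 4 also applies to either group, and item 5 reads "5 patients that show greater than 4 point deterioration in MMSE in two consecutive cognition evaluations".

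The rule gates escalation. Once the first cohort's 12-month follow-up is complete, the Schema sets this condition: "there have been no events that cause stoppage of the trial, the second group of patients will be enrolled at Dose Level 2".

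Section 3.5 gives 7 points as a proposed mark of clinically significant ADAS-Cog change. Section 3.10 quotes, for placebo patients of an earlier trial, a mean one-year worsening of 5.7 points (SD 8.2). No section compares rule 6 with that decline.

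**The concern.** A mandatory rule with two texts cannot be applied consistently. Someone working from the Schema and someone working from section 3.12 could look at the same scores and reach opposite decisions about continuing and escalating.

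The second worry is where the threshold sits. Seven points is only 1.3 points above the mean worsening the protocol expects in a year without treatment, and the spread of that worsening is wide. A rule that counts individual patients above 7 could therefore be met by disease progression alone. With no control group, the trial has no internal way to tell that from harm. At stake are whether Dose Level 2 opens and how a stop would be interpreted.

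**Working it through.** **The plan's own figures.** The quoted decline is consistent with its parts: 29.9 − 24.2 = 5.7. The one design calculation, in section 3.1, gives upper limits for zero events in 15 patients. It reproduces as 1 − (1 − confidence)^(1/15) = 26.4%, 18.1% and 14.2% at 99%, 95% and 90%. Nothing similar is given for rule 6.

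**The two texts can disagree.** Take a patient who worsens linearly to 10 points at 12 months. The visits in section 3.10 are at 6 weeks and 3, 6 and 12 months, that is 0.125, 0.25, 0.5 and 1 year, averaging 0.469. That patient's mean increase over visits is 10 × 0.469 = 4.7. Five such patients meet section 3.12's wording at 12 months. They do not meet the Schema wording read as a mean over each patient's visits.

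**Section 3.12 wording, no harm from treatment.** Inputs: mean 5.7 and SD 8.2 (section 3.10), cut at 7, at least 5 patients. Section 3.9 says that patients who do not finish radiotherapy "will be replaced in the study in order to have 15 evaluable patients in each arm". Assumptions: normal change, independent patients, 12-month visit.

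- p = 1 − Φ((7 − 5.7)/8.2) = 0.437, so 15 × 0.437 = 6.6 patients expected above 7.
- P(at least 5 of n) = 1 − BinomCDF(4; n, p) = 0.858 for n = 15, 0.807 for 14, 0.742 for 13 and 0.663 for 12.

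Sensitivity:

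- Assumed means 4 to 7.5 and SDs 6 to 10: 0.51 to 0.97 for n = 15; 0.30 to 0.86 for n = 12.
- Right skew (Pearson III, same mean and SD): skew 1 gives p = 0.374, hence 0.72 (n = 15) and 0.49 (n = 12). Skew 2 gives p = 0.314, hence 0.53 and 0.31. Left skew raises the figures: skew −1 gives 0.94 for n = 15.
- If a rise at any of the four visits counts (assumed linear decline, error SD 0 to 5): 0.86 to 0.99 for n = 15.
- If the count runs over both groups (n = 30): 0.9996.

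**Schema wording, read as each patient's mean over the four visits.** Model: change at time t = S·f(t) + visit error − baseline error, where S has mean 5.7 and variance 8.2² − 2e², and e is the assumed error SD (0 to 5). With f̄ the average of f over the visits, a patient's mean change has mean 5.7·f̄ and variance (8.2² − 2e²)·f̄² + 1.25·e².

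| Assumed shape | f̄ | Mean | p, e = 0 to 5 | P(at least 5 of 15) |
|---|---|---|---|---|
| linear, t | 0.469 | 2.67 | 0.130 to 0.232 | 0.04 to 0.26 |
| quadratic, t² | 0.332 | 1.89 | 0.030 to 0.187 | 0.00 to 0.13 |
| square root, √t | 0.640 | 3.65 | 0.262 to 0.294 | 0.35 to 0.46 |

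Section 3.10 plans a model "using a fixed quadratic effect of time, dependent on the baseline level of ADAS-Cog" but gives no coefficients, so the documents do not fix the shape.

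**What a stop would tell.** With an assumed 3 points of added decline, section 3.12's wording gives p = 1 − Φ((7 − 8.7)/8.2) = 0.582 and P(at least 5 of 15) = 0.99, against 0.86 with no harm.

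**The case against.** Four points on the other side have weight.

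- **A safety gate may be deliberately sensitive.** This is a first study of brain irradiation in these patients, and a low bar for stopping is defensible. The protocol does not say that this was the intent, however, and intent would not explain two wordings.
- **There is human judgement in the loop.** Under section 5.0 the DSMB is advisory and may recommend continuing or modifying the study. Section 3.9 lets it attribute an increase of 2 or more points to non-study causes, with accrual resuming after IRB clearance. That route is written for toxicity points and is not expressly tied to rule 6. Part of section 5.0 is missing from the available text. These provisions soften the consequence but do not settle which rule applies.
- **The reference decline may not transfer.** Section 3.10 gives a baseline of 24.2 (SD 9.4) for patients in a range of 13 to 26. The largest SD possible there is √((24.2 − 13) × (26 − 24.2)) = 4.5, so the population is unclear. Section 3.10 also says that the rate of change depends on severity. The bias could go either way. The replacement rule does not cover dropout after radiotherapy, hence the figures for 12 patients.
- **The study is descriptive.** Section 3.1 disclaims hypothesis testing, and nothing commits the sponsor to reporting stopping probabilities. That part of the fix is a recommendation; the conflict needs correcting regardless.

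A reader might go further and infer that rule 6 is a lack-of-benefit rule, because section 3.10 reports that in the cited trial "a significant benefit in the active group was considered to be a 50% reduction in cognitive decline". No section links that benchmark to rule 6, and section 2.3 uses ADAS-Cog to supplement toxicity assessment. A reader might also take the Schema's mean as an average over the whole cohort, but that ignores its words about 5 patients.

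**Conclusion.** The conflict is certain: two current, mandatory texts of one rule, with no stated precedence and undefined visit, group and averaging. It matters because the texts behave very differently under the decline the protocol quotes. On these models section 3.12's wording would probably be met without any harm, at about 0.86 with 15 evaluable patients and 0.66 with 12. The Schema wording, as a patient mean over visits, would be met less than half the time.

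The probabilities carry moderate confidence. They rest on the quoted decline applying here, approximate normality, independence and the 12-month visit. With 12 evaluable patients and either slower decline or marked right skew, the section 3.12 figure falls to about 0.3, so *probably* is not *certainly*.

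A reader might infer that the trial is bound to stop before Dose Level 2, or that a stop would waste the first cohort. The documents support neither. The sponsor's and DSMB's discretion is only partly visible, and the Dose Level 1 toxicity data, which are the primary endpoint, would largely remain. The supported statement is that natural decline alone could trigger the stop under section 3.12.

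**What to change.** Reconcile the Schema and section 3.12 into a single text of rule 6. The sponsor and DSMB should define which visit or visits count, whether counting is per dose group, and whether any averaging or confirmation applies. The protocol should then state the probability that the reconciled rule is met under the decline quoted in section 3.10, with the assumptions shown. This review proposes no threshold, count or visit and does not say which version is right.

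The cost is a wording change and a short calculation, with no extra patients, visits or tests. The small downside is that the sponsor and DSMB must openly weigh false stops against missed harm, and may have to publish an unfavourable figure.

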#### **4.0 Risks and Benefits**

Patients will be advised that the use of radiation to treat Alzheimer's disease has not been reported and such treatment should be considered investigational. There is the possibility that treatment-related adverse events may be observed. Close monitoring with frequent assessment of toxicity and signs of progression will be performed and reported. There is the possibility that radiation treatment may improve cognitive decline resulting in benefit for the patient.

#### **5.0 Data Safety Monitoring Plan**

The appointed Data Safety and Monitoring Board (DSMB) will act in an advisory capacity to the IDE Sponsor/Investigator and the Beaumont Research Institute to monitor participant safety, data quality and evaluate the progress of the study.

The DSMB will consist of four members (three voting, one non-voting) who are not directly involved in the trial and have expertise in the fields of radiation and/or Alzheimer's disease management, clinical trial methodology, and/or biostatistics. Prior to implementation of the protocol, the DSMB will meet to review the protocol and informed consent documents, approve templates for study summary reports, and to adopt the charter.

The DSMB will review cumulative study data to evaluate safety, study conduct, and scientific validity and integrity of the trial. Meetings of the DSMB may occur as frequently as monthly during the enrollment and treatment phase of the trial. Monthly meetings will be scheduled, however, prior to each meeting, the DSMB Chair will review the agenda. If there are no new enrollments, additional study data, or updates from the IDE Sponsor/Investigator, the DSMB Chair may cancel the meeting.

After enrollment has stopped, the DSMB will meet quarterly. The DSMB will discharge itself from its duties when the last participant completes the study.

The DSMB Chair will provide a written report after each meeting containing DSMB recommendations as to whether the study should continue without change, be modified, or terminated. The DSMB Chair will provide the written report to the IDE Sponsor/Investigator and the Beaumont Research Institute. The IDE Sponsor/Investigator will submit the report to the Site Investigator(s) and the FDA. The Site Investigator(s) will submit the reports to their respective IRBs.

Along with meeting at regular intervals during the conduct of the trial, the DSMB will meet within one week of any adverse event that increases by 2 or more points according to the

## 6.0 Study Calendar

	Pre Treatment	Daily Radiation Treatment	6 Weeks Post Treatment +/- 1 week	Post Treatment (Months)			
				3 +/- 2 weeks	4 +/- 2 weeks	6 +/- 2 weeks	12 +/- 2 weeks
ADAS-Cog	X		X	X		X	X
MMSE	X		X	X		X	X
History & Physical	X		X	X		X	X
AMYViD PET scan	X				X		
Toxicity Evaluation	X	X	X	X		X	X
QOL-AD and QUALID	X		X	X		X	X

## Appendix I: Eligibility Checklist

Patient No: \_\_\_\_\_ Patient Name: \_\_\_\_\_

### **Inclusion Criteria for Eligibility (All responses must be Yes)**

**Yes    No**

- \_\_\_\_\_ 1. Patient is 55 years of age or older
- \_\_\_\_\_ 2. Patient meets NINCDS-ADRDA criteria for Alzheimer's Disease
- \_\_\_\_\_ 3. Patient must be able to complete Mini-Mental Examination and ADAS-Cog Score Sheets
- \_\_\_\_\_ 4. Patient has a Rosin Modified Hachinski Ischemic Score of less than or equal to 4
- \_\_\_\_\_ 5. Patient has a MMSE score of between 10-20
- \_\_\_\_\_ 6. Patients has estimated survival of greater than 12 months
- \_\_\_\_\_ 7. Patient or legally authorized representative is able to give consent

Investigator Signature \_\_\_\_\_

Date \_\_\_\_\_

**Exclusion Criteria for Eligibility (All responses must be No)**

**Yes    No**

- 1. Patient has a history of cancer except non-melanoma skin cancer
- 2. Patient is taking anti-epileptic medication.
- 3. Patient has dermatological skin disease (lice, ringworm, eczema, or psoriasis) of the scalp
- 4. Patient is taking Alzheimer medication within the last 3 months, i.e. Exelon, Aricept, Namenda, Reminyl or Epixa.
- 5. Patient has current presence of a clinically significant major psychiatric disorder (e.g. major depressive disorder, bipolar illness, schizophrenia, etc., according to DSM-IV)
- 6. Patient is currently participating in another Clinical Trial.
- 7. Patient and legally authorized representative are unable to give informed consent
- 8. Patient has history of focal neurological deficits (with the exception of vibratory peripheral neuropathy)
- 9. Patient has non-Alzheimer dementia
- 10. Patient has previous history of CNS radiation
- 11. Patient has evidence of substance abuse (alcohol / or other drugs of dependence) during the previous 12 months
- 12. Patient has history of subdural hygroma / subdural hematoma
- 13. Patient has history of cerebral infection / hemorrhage
- 14. Patient has history of being immunocompromised
- 15. Patient has history of seizure activity
- 16. Patient has history of hydrocephalus

---

Investigator Signature

---

Date

## Appendix II: NINCDS-ADRDA Score

[https://www.alzheimersanddementia.com/article/S1552-5260\(11\)00101-4/fulltext](https://www.alzheimersanddementia.com/article/S1552-5260(11)00101-4/fulltext)

## Appendix III: CTCAE V.5.0 criteria for assessment of anticipated toxicity

## ALZHEIMER DISEASE RT STUDY TOXICITY WORKSHEET

Date \_\_\_\_\_

ID# \_\_\_\_\_ Name \_\_\_\_\_ MD \_\_\_\_\_

Physician Signature: \_\_\_\_\_ Date/Time: \_\_\_\_\_

**Skin Toxicity:****Radiation recall reaction (dermatologic)**

- Grade 0, None
- Grade 1, Faint erythema or dry desquamation
- Grade 2, Moderate to brisk erythema; patchy moist desquamation mostly confined to skin folds and creases; moderate edema
- Grade 3, Moist desquamation in areas other than skin folds and creases; bleeding induced by minor trauma or abrasions
- Grade 4, Life threatening consequences; skin necrosis or ulceration of full thickness dermis; spontaneous bleeding from involved site; skin graft indicated

**Alopecia**

- Grade 0, None
- Grade 1, Hair loss <50% normal for that individual; not obvious from distance but only on close inspection
- Grade 2, Hair loss >50%; wig/hair piece need if patient desires to completely camouflage hair loss associated with psychosocial impact

**Xerostomia**

- Grade 0, None
- Grade 1, Symptomatic (dry or thick saliva) without significant dietary alteration, unstimulated saliva flow > 0.2 ml/minute
- Grade 2, Moderate symptoms, oral intake alteration (copious water, other lubricants, diet limited to purees and/or soft, moist foods); unstimulated saliva flow 0.1-0.2 ml/minute
- Grade 3, Inability to adequately aliment orally (IV fluids, tube feedings, or TPN indicated), unstimulated saliva flow < 0.1 ml/minute

 **Other skin toxicity not listed above** \_\_\_\_\_**Eye Toxicity:****Blurred Vision**

- Grade 0, None
- Grade 1, Intervention not indicated
- Grade 2, Symptomatic; limiting instrumental ADL
- Grade 3, Limiting self care ADL

**Cataract**

- Grade 0, None
- Grade 1, Asymptomatic; intervention not indicated
- Grade 2, Symptomatic; moderate decrease in visual acuity (20/40 or better)
- Grade 3, Symptomatic with marked decrease in visual acuity-operative intervention indicated
- Grade 4, Blindness (20/200 or worse) in affected eye

 **Other eye toxicity not listed above** \_\_\_\_\_

**Ear Toxicity:**

**Ear Pain (Definition: a disorder characterized by a sensation of marked discomfort inside the ear)**

- Grade 0, None
- Grade 1, Mild pain
- Grade 2, Moderate pain; limiting instrumental ADL
- Grade 3, Severe pain; limiting self care ADL

**Hearing Loss**

- Grade 0, None
- Grade 1, Subjective change in hearing in the absence of documented hearing loss
- Grade 2, Hearing loss but hearing aid or intervention not indicated; limiting instrumental ADL.
- Grade 3, Hearing loss with hearing aid or intervention indicated
- Grade 4, Decrease in hearing to profound bilateral loss; non-servicable hearing.

Additional hearing loss since treatment  No  Yes

Other ear toxicity not listed above \_\_\_\_\_

